11.4.5 Safety analysis

The study team will provide a descriptive analysis of all reported adverse events. The analysis will focus on the type of event, duration, and timing and relate the number of observed events to the number of rTMS sessions administered. Furthermore, the frequency of adverse events will be compared between treatment arms of the trial.

11.4.6 Deviation(s) from the original statistical plan

Any deviation from the statistical plan will be reported and justified in the methods of the study report.

11.5 Handling of missing data and drop-outs

We will apply the last-observation-carried-forward (LOCF) method in the final analyses. In case a patient withdraws consent before the first rTMS stimulation, we will recruit an additional patient. The number of all patients recruited and randomized will be reported in the publications.

Sensitivity analyses will be performed in order to establish whether premature dropout would influence the results. Therefore, the primary analyses will be repeated with all subjects who completed the interventional trial. Further tests will establish whether drop-outs differ from completers in basic clinical or demographic variables.

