6.3 Unblinding Procedures (Code break)

In case of severe adverse events, an unblinding can take place at the responsibility of the principal investigator. In this case, the participant will not be able to further participate in the study. The allocated intervention order will be kept in a sealed envelope. The sealed envelopes will be stored at a central place, i.e. the office of the lab, so they can be accessed in case of any emergency.

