7.4 Criteria for withdrawal / discontinuation of participants

Participants may discontinue the trial at any time or withdraw consent. Furthermore, the treating physicians may request study discontinuation in case of significant deterioration of the condition at any time during the intervention period. All data from subjects in the intent-to-treat population, who received at least one dose of rTMS will be further used in the analyses. We will apply the last-observation-carried-forward (LOCF) method in the final analyses. In case a patient withdraws consent before the first rTMS stimulation, we will recruit an additional patient. The number of all patients recruited and randomized will be reported in the publications. All data from neuroimaging acquisition and motor behaviour will be used whenever possible, e.g. for analyses of baseline associations between brain imaging and behavior. In case of withdrawal due to adverse events or serious adverse events there will be follow-up examinations after 14 days and repeatedly until the problem is resolved, see 9.2.5.

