8.3 Dose / Device modifications

In case of intolerable side effects, the study will be discontinued for the participant. No dose or device modifications are planned.

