8.4 Compliance with study intervention

Investigators have to document the order of stimulation. This will be checked for consistency with the group allocation. No further strategies are needed. Participants are always under observation during the rTMS sessions and the planned assessments. Non-compliance on the side of the participant would lead to study discontinuation for this person. Use of concomitant medication will be retrieved from the medical files of the patients and transferred to the CRF.

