8.5 Data Collection and Follow-up for withdrawn participants

If participants withdraw their consent, they will be contacted immediately to clarify whether there were intolerance issues with the study. See section 9.2.5 for safety follow-up measures. In case of withdrawal the data will be analyzed and stored encrypted as all the data of the other participants. However, we will remove the encryption key for the participants who withdrew consent and therefore it will not be possible to identify the subjects from encrypted data. Patients who withdrew consent will be invited for the 6 month follow-up interview using their preferred way of contact (Email, letter).

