9.2.4.3 Vital signs

No routine measurement of vital signs is planned. If patients report dizziness, clinical routines will include measurement of blood pressure and heart rate.

9.2.5 **Assessments in participants who prematurely stop the study**

Participants who prematurely stop the study will be immediately assessed for adverse events. In case of adverse events reports, a physical examination will be conducted and results will be recorded accordingly. Follow-up examinations will be planned within the next 14 days in case of continuing problem related to adverse events, and these examinations will be continued every 14 days until the health issue is resolved.

9.3 **Procedures at each visit**

9.3.1 **Screening visit**

- Check the inclusion and exclusion criteria, use CRF
- Collect demographic data, use CRF
- Conduct urine pregnancy test in female participants between 18 and 50 years of age
- Assess diagnoses with SCID, document results in CRF
- Assess handedness with EHI¹⁰¹, document result in CRF
- Assess medical history in CRF

See table study events at 9.1

9.3.2 **Visit 2 (baseline, week 0)**

- Assess current psychopathology, use PANSS interview and BNSS, document in CRF
- Assess formal thought disorder, use TALD interview, document in CRF
- Assess Neurological soft signs, use NES, document in CRF
- Assess psychiatric history with CASH interview in patients, document result in CRF
- Assess primary outcome with SRRS scale, document in CRF
- Assess motor behaviour with rating scales, use BFCRS, UPDRS, AIMS, document results in CRF
- Assess functioning, use GAF, SOFAS, and UPSA-brief, document results in CRF
- Hand out self-rating questionnaires SNS and IPAQ, collect and document in CRF
- Conduct coin rotation test, record on video
- Record gross motor activity using actigraphy
- Test cortical excitability using the TMS device according to standard procedure. Record electronic data
- Acquire MRI scans at University Institute of Diagnostic and Interventional Neuroradiology
- Acquire posturography at University Hospital, Dept. of Neurology, record electronic data
- Record current medication regime in CRF
- Schedule 5 rTMS sessions
- Schedule next visit

9.3.3 **Visit 3 and 4 (week 1 and 2)**

- Assess primary outcome with SRRS scale, document in CRF
- Assess side effects with questions in the CRF
- Record current medication regime in CRF
- Schedule 5 rTMS sessions
- Schedule next visit

9.3.4 **Visit 5 (end of intervention, week 3)**

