11.4.2 Primary Analysis

The primary analysis will be a repeated measures ANOVA of SRRS scores with two timepoints (within

subjects: baseline and week 3) and four groups (lf-rTMS, iTBS, sham, waiting group-If-rTMS). In case of significant baseline demographic or clinical group differences, we will adjust for these in an repeated measures ANCOVA of SRRS.

The analysis will be performed by the PI and his team in SPSS using data from the RedCap database.

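### For patients who stop early in the three immediately stimulated arms, LOCF enters an earlier SRRS score as week 3; at low drop-out the bias is modest, it can go either way, and it is cheap to reduce.

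*Combined protocol and SAP*

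**What the plan says.** Section 11.5 sets the missing-data rule: "We will apply the last-observation-carried-forward (LOCF) method in the final analyses". Section 7.4 repeats it. Section 11.4.2 defines the main test: "The primary analysis will be a repeated measures ANOVA of SRRS scores with two timepoints", namely baseline and week 3, in four groups. Section 11.4.1 restricts the analysis of rTMS effects to patients who had one or more rTMS sessions. Sections 8.1.2 and 8.2.2 start stimulation in the waiting arm only after week 3. Section 5.1 and the schedule in 9.1.1 place SRRS ratings at weeks 0, 1, 2 and 3 in groups 1-3.

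Four sections describe ways out of the study:
- 7.4: "the treating physicians may request study discontinuation in case of significant deterioration of the condition at any time during the intervention period".
- 6.3, after unblinding: "In this case, the participant will not be able to further participate in the study".
- 8.3: "In case of intolerable side effects, the study will be discontinued for the participant".
- 8.4: "Non-compliance on the side of the participant would lead to study discontinuation for this person".

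After an early stop, 9.2.5 says "Participants who prematurely stop the study will be immediately assessed for adverse events". Section 10.1.3 adds follow-up of adverse events, and 8.5 adds an invitation to the 6-month interview. None of these names an SRRS rating at stopping or at week 3.

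As a check, 11.5 repeats the primary analysis in completers and compares drop-outs with completers on basic clinical and demographic variables.

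**The concern.** The primary ANOVA needs a week-3 score from every patient. For an early stopper in groups 1-3 the plan offers only an older one: baseline, week 1 or week 2. That score enters as the end-of-course result although part of the course, and part of any improvement, was still to come. The waiting arm is not treated alike, because a patient there joins the analysis set only after reaching week 3. LOCF therefore alters three of the four groups being compared.

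At stake is the size of the lf-rTMS effect and, to a lesser degree, the four-group test. The week-1 and week-2 ratings that would support a better method are already scheduled, but the primary ANOVA uses them only as carried values.

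**Working it through.** **1. The plan's own figure.** Inputs from 11.2: f = 0.23, correlation 0.5, alpha 0.05, power 0.95, four groups, two time points. For the group-by-time interaction, lambda = f² × N × m / (1 − rho) = 0.0529 × 88 × 2 / 0.5 = 18.62. With F(3, 84), power is 0.957, so 88 reproduces. On change scores f is √(18.62/88) = 0.46. If one arm differs from three equal arms, the difference is 0.46 / √(3/16) = 1.06 SD. Section 11.2 mentions no drop-out allowance.

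**2. LOCF in closed form.** Let D be the true lf-rTMS versus placebo effect, b the improvement common to both arms, p the share stopping early, and r the share of change still to come at the last rating. Then

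LOCF estimate = (b + D)(1 − p_lf × r) − b(1 − p_pl × r).

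Assumed: D = 0.80 SD and r = 1/2 (linear change, last rating equally often at week 1 or week 2). The documents give neither drop-out rates nor b.

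| Drop-out lf / placebo | b (SD) | Calculation | Estimate (SD) |
|---|---|---|---|
| 5 / 5% | any | 0.80 × 0.975 | 0.78 |
| 15 / 15% | any | 0.80 × 0.925 | 0.74 |
| 10 / 5% | 0.2 | 1.0 × 0.95 − 0.2 × 0.975 | 0.755 |
| 25 / 10% | 0.2 | 1.0 × 0.875 − 0.2 × 0.95 | 0.685 |
| 5 / 10% | 0.2 | 1.0 × 0.975 − 0.2 × 0.95 | 0.785 |
| 10 / 25% | 0.2 | 1.0 × 0.95 − 0.2 × 0.875 | 0.775 |
| 10 / 25% | 1.0 | 1.8 × 0.95 − 1.0 × 0.875 | 0.835 |

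**3. When the sign flips.** The estimate exceeds D when p_pl > p_lf and b > D × p_lf / (p_pl − p_lf).
- 10/25%: 0.80 × 0.10 / 0.15 = 0.53 SD; with D = 0.40 it is 0.27 SD.
- 1 of 22 versus 5 of 22: 0.80 × 1/4 = 0.20 SD.
- No lf-rTMS stoppers: zero, so any common improvement inflates. At a 5% rate an arm of 22 has no stoppers with probability 0.95^22 = 0.32.

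**4. Scale.** At correlation 0.5 the SD of change equals the SD, so the contrast's standard error is √(2/22) = 0.30 SD. With no true effect the bias is r × (p_pl − p_lf) × b: zero at equal drop-out, and 0.015 to 0.075 SD at 10/25% with b from 0.2 to 1.0 SD. Simulated four-group null rejection under LOCF is 4.5-5.5% with b = 0.2 SD and at most 7.7% (10/25%, b = 1.0 SD).

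**5. Heavier loss.** Take D = 1.06 SD, the last rating equally often at week 0, 1 or 2 (r = 2/3), and equal drop-out in groups 1-3. At 5, 10, 20 and 30% the contrast with placebo is 1.03, 0.99, 0.92 and 0.85 SD. Four-group power is 0.94, 0.93, 0.89 and 0.83 with b = 0, and 0.93, 0.89, 0.80 and 0.70 with b = 1.0 SD. The contrast with the waiting arm shrinks more, because that arm's scores are not carried: D − p × r × (b + D) = 1.06 − 0.3 × 2/3 × 2.06 = 0.65 SD at 30% and b = 1.0 SD.

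**6. LOCF against completers and a mixed model.** Simulation with 22 per arm, truth 0.80 SD, b = 0.2 SD, correlations 0.8/0.65/0.5, linear change, stopping after week 1 or 2, iTBS drop-out equal to placebo, 1,500 runs per cell (Monte Carlo error about 0.008 SD). Linking drop-out to SRRS is an assumption.

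| lf / placebo | Drop-out follows observed SRRS: LOCF / completers / mixed | Drop-out follows unobserved next score: LOCF / completers / mixed |
|---|---|---|
| 10 / 5% | 0.75 / 0.85 / 0.80 | 0.79 / 0.87 / 0.83 |
| 15 / 15% | 0.74 / 0.805 / 0.80 | 0.74 / 0.80 / 0.80 |
| 25 / 10% | 0.68 / 0.935 / 0.80 | 0.75 / 0.99 / 0.89 |
| 10 / 25% | 0.79 / 0.67 / 0.80 | 0.72 / 0.615 / 0.715 |

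LOCF and completers bracket or touch 0.80 in six of the eight cells; the exceptions are both at 10/25%. Under random drop-out, four-group power for LOCF versus the mixed model is 0.931 versus 0.947 at 15/15% and 0.954 versus 0.951 at 10/25%.

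**The case against.** **The problem may be small.** This is a three-week, mainly inpatient trial under close observation. Section 3.4 reports that iTBS was well tolerated, and 3.7 reports no deterioration and one unrelated serious event in the prior trial. This stands, with a limit. If 3.7 refers to the 34 patients of 3.1.7, zero events leaves a one-sided 95% upper limit of 1 − 0.05^(1/34) = 8.4%, or 12.7% for the 22 with schizophrenia. Stopping for side effects or non-compliance comes on top.

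**The target is unstated.** Shrinkage is measured against a completed course. Section 2.2 anticipates benefit persisting two to four weeks beyond the final session, so a stopper's last score may lie near the real week-3 score. If the target includes early stopping, the bias is smaller. This stands.

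**The mixed model is not always better.** When drop-out follows unobserved scores, the errors in step 6, in table order, are −0.01, −0.06, −0.05 and −0.08 for LOCF, and +0.03, 0, +0.09 and −0.085 for the mixed model. This stands, and it is why the model alone is not the whole remedy.

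**Stronger readings that do not hold.** A reader might infer that LOCF is always conservative here, or that it inflates only when common improvement is large. Step 3 shows the threshold can be small or zero. A reader might also infer that the planned completer analysis and drop-out comparison are worthless. They help: completers are unbiased under random drop-out, and bracketing failed only where placebo lost far more patients through outcome-linked drop-out, a pattern nothing in the documents predicts.

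**Conclusion.** The point holds as a modest one. By the plan's rules, an early stopper in groups 1-3 enters the primary ANOVA with a week-0, -1 or -2 score labelled week 3, while waiting-arm patients in the set have observed week-3 scores. Against the effect of a completed course, LOCF shrinks a real lf-rTMS versus placebo effect when drop-out is equal or higher under lf-rTMS. With more placebo drop-out it can inflate the effect, under the condition in step 3.

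At an assumed 5-15% equal drop-out and D = 0.80 SD the bias is 0.02-0.06 SD, against a standard error of 0.30 SD. It becomes material only at rates that the documents give no reason to expect. All sizes rest on assumed drop-out, linear change and assumed common improvement. The documents do not support a claim that the trial is underpowered or its test invalid because of LOCF: 88 patients still fits, and power is not the reason to change. The reason is that a better use of ratings already scheduled costs little.

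**What to change.** **Analysis.** In 11.4.2, 11.5 and 7.4, with matching words in the synopsis and 11.2:
- Make the primary analysis a likelihood-based mixed model (SPSS MIXED, unstructured covariance) of all observed SRRS ratings at weeks 0, 1, 2 and 3, or weeks 0 and 3 for the waiting arm.
- Keep the four-group, 3-degree-of-freedom test of change from baseline to week 3 as primary. Write this contrast out, since a default group-by-week test would also cover weeks 1 and 2.
- Carry over the covariate-adjustment provision of 11.4.2.
- Report the week-3 lf-rTMS versus placebo and lf-rTMS versus iTBS contrasts from the same model.
- State the target: the effect had treatment been completed, or the effect regardless of early stopping. Any use of post-stop ratings must match it.
- Keep LOCF and completers as sensitivity analyses. Add one that worsens imputed week-3 scores of drop-outs in fixed steps until the conclusion changes, first in the lf-rTMS arm only, then in all stimulated arms.

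**Data.** Where the patient still consents, collect the already scheduled SRRS through week 3 after stimulation stops. Sections 6.3, 8.3 and 8.4 end study participation, so they must be reconciled with this. When stimulation stops does not change.

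**Cost.** The model change is wording, in software already named, with N = 88 unchanged. Post-stop ratings need an amendment, with prior ethics approval under 2.10 if substantial, and a few 5-minute ratings. The mixed model assumes that drop-out depends on observed scores and is not reliably closer than LOCF when unequal drop-out depends on unobserved ones. Waiting-arm patients who leave before week 3 stay outside the analysis set; this change does not address them.

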2.2 Categorisation of study

The trial is in Risk Category A. There is only minimal risk associated with the trial. The TMS device has CE certification and approved for clinical use. It will be applied according to the manual and guidelines^{1, 2}. TMS has been widely used in neuroscience, and in clinical trials on depression, schizophrenia and chronic pain. Participants will receive 15 daily stimulations. Effects are expected to last for 2-4 weeks after the last stimulation. TMS is also safe in repeated administration^{1, 2}.

Assessments include standard clinical rating scales, short specific tests of motor behaviour, and a standard cerebral magnetic resonance imaging at baseline and after 3 weeks of stimulation. All assessments have been applied to schizophrenia patients before and are generally well tolerated.

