4.3 Secondary Objectives

The study further seeks to determine, whether lf-rTMS (inhibitory) will be superior over placebo or iTBS (facilitatory) in all clinical and motor behavioral measures, e.g. greater reduction in BFCRS scores from baseline, greater increase in activity levels, or finger taps. In addition, the study will test the effects of rTMS on the cerebral motor network connectivity and activity, as well as on cerebellar function and motor cortex excitability. Furthermore, the study will explore the neuroimaging markers of response to treatment. Moreover, the study will test the association between measures of PS and neuroimaging markers of the motor system, e.g. network connectivity, activity, and structure. Next, the study will investigate the temporal dynamics of PS by comparing a waiting list group to the placebo group. Finally, the study will test whether lf-rTMS treatment for 3 weeks will have lasting effects on PS at week 6 or 6-months follow-up.

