5. STUDY OUTCOMES

5.1 Primary Outcome

The primary outcome variable is the SRRS score as a surrogate marker of psychomotor slowing. The primary endpoint will be the change SRRS ratings from baseline to week 3 measured with the SRRS⁹². The SRRS is administered at baseline, week 1, week 2, week 3, week 6, and week 24. It is an observer rated scale quantifying the severity of psychomotor slowing with 15 items, each ranging 0-4. The SRRS has been developed to target this behavior and has been used in previous trials. Assessments will be performed by blinded raters, who have been trained to use the scale reliably.

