5.2 Secondary Outcomes

5.2.1 Clinical outcomes

Proportion of responders ($\geq 30\%$ reduction from baseline SRRS) between groups at week 1, 2, 3, 6, and 24. This will provide an additional categorical measure of who benefits from the intervention in terms of the main target (psychomotor slowing).

Change in other commonly observed motor symptoms from baseline, including rating scales on

abnormal involuntary movements, Parkinsonism, and catatonia at week 3, 6, and 24. See section 9 for details on instruments.

Change in general psychopathology using the positive and negative syndrome scale PANSS⁹³ and the brief negative symptom scale BNSS⁹⁴ between baseline and week 3, week 6, and week 24.

Change in self-reported physical activity and experienced negative symptoms using the International Physical Activity Questionnaire (IPAQ)⁹⁵ and the self-evaluation of negative symptoms (SNS)⁹⁶.

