Hypothesis 4a: patients receiving inhibitory rTMS will have better outcome (less PS, less general symptom severity) shortly after the intervention (at 6 week follow-up) compared to patients receiving placebo or facilitatory iTBS

Hypothesis 4b: patients receiving inhibitory rTMS will have better outcome (less PS, less general symptom severity) and superior function (social and global) at 6-month follow-up compared to patients receiving placebo or facilitatory iTBS

Hypothesis 4c (exploratory): changes in functional connectivity within the motor system from baseline to week 3 will predict better outcome at week 6, particularly reduced M1-thalamus functional connectivity.

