11.4.3 Secondary Analyses

Secondary analyses focus on the secondary outcomes (see 5.2) and hypotheses (see 11.1).

Crosstabs are used to calculate the proportion of responders ($\geq 30\%$ reduction in SRRS from baseline) across groups. Repeated measures ANOVAs will clarify the time-course of SRRS change from baseline to week 6 (including week 1, 2, 3 and 6) and differences between groups.

Repeated measures ANOVAs will test the change of clinical and motor rating scales between baseline and week 3, week 6, and week 24 and differences between groups.

Linear regression analyses will test the association between neuroimaging markers (resting state perfusion, connectivity, fMRI activation, ect.) and measures of PS at baseline.

Repeated measures ANOVAs will test the longitudinal changes in neuroimaging markers from baseline to week 3.

All analyses will be performed by the PI and his team or collaborators with permission of the PI.

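### LOCF has no visit limit, so a week-3 or week-6 symptom score can stand in for week 24, where the plan tests whether benefit lasts

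*Combined protocol and SAP*

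**What the plan says.** Section 11.5 states: "We will apply the last-observation-carried-forward (LOCF) method in the final analyses". Section 7.4 repeats the rule. Neither limits it to week 3, and no other missing-data method appears for the follow-up visits.

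Week 24 is an analysed visit. In section 5.1, "The SRRS is administered at baseline, week 1, week 2, week 3, week 6, and week 24". Section 5.2.1 compares responder proportions "between groups at week 1, 2, 3, 6, and 24". In section 11.4.3, "Repeated measures ANOVAs will test the change of clinical and motor rating scales between baseline and week 3, week 6, and week 24", with group differences. The synopsis lists change in PANSS, BNSS, SRRS and SOFAS to 6 months as an outcome. Section 4.3 asks whether three weeks of lf-rTMS "will have lasting effects on PS at week 6 or 6-months follow-up". Hypothesis 4b expects less slowing, milder symptoms and "superior function (social and global) at 6-month follow-up compared to patients receiving placebo or facilitatory iTBS".

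On duration, section 2.2 says: "Effects are expected to last for 2-4 weeks after the last stimulation".

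The one sensitivity analysis, in section 11.5, repeats the primary analysis in patients who completed the intervention. Under section 11.4.2, the primary analysis covers baseline and week 3.

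**The concern.** For a patient who finishes treatment and does not return, LOCF presents the end-of-treatment or week-6 rating as the 6-month result. For that patient, durability is assumed and not measured. In groups 1-3 week 24 is 21 weeks after treatment ends (24 - 3), while section 2.2 places the expected effect at about weeks 5 to 7 (3 + 2 to 3 + 4).

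This is a different problem from dropout before week 3, which bears on the primary endpoint. Here the patient counts as a completer and the question is whether benefit lasts. At stake are the lasting-effect objective, hypothesis 4b and the week-24 responder comparison. Each could look better than the data warrant because of loss to follow-up.

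**Working it through.** **1. The plan's own figure, used to set the scale.** Inputs from section 11.2: f = 0.23, correlation 0.5, alpha 0.05, power 0.95, four groups, two time points. For the group-by-time interaction, lambda = f² × N × 2 / (1 - 0.5). At N = 88 this is 0.0529 × 88 × 2 / 0.5 = 18.62, with 3 and 84 degrees of freedom and power 0.957. N = 84 gives 0.947, so 88 is reproduced.

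**2. Conversion to a week-3 difference.** With correlation 0.5 the SD of a change score equals the SD of a score. On the change scale f = √(18.62/88) = 0.46. Two patterns of means give a range for lf-rTMS versus placebo:
- Only lf-rTMS differs: the SD of the four means is δ√3/4, so δ = 0.46 × 4/√3 = 1.06 SD.
- lf-rTMS and iTBS lie at opposite ends, with the other two arms midway: the full range is 0.46 × 2√2 = 1.30, so lf-rTMS versus placebo is 0.65 SD.

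**3. Bias formula.** Let d be the share of each arm lost before week 24 and E the effect at the carried visit. With no true week-24 difference, the LOCF difference is d × E. For example, 0.30 × 1.06 = 0.32 SD. If the score is carried from week 6 with half the effect left, it is 0.30 × 0.53 = 0.16 SD.

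**4. False-positive rates.** Assumptions: 22 per arm, change scores with SD 1 and correlation 0.5 between visits, no true week-24 difference, equal random loss, two-sided 5% t-test of lf-rTMS against placebo, 200,000 simulated trials per setting. The documents give no loss rate, so d is a range. The half-effect at week 6 is also assumed.

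| Week-3 effect | Score carried from | d = 10% | 20% | 30% | 40% |
|---|---|---|---|---|---|
| 1.06 SD | week 3 | 6.3% | 10.0% | 16.4% | 25.3% |
| 1.06 SD | half week 3, half week 6 | 5.8% | 8.0% | 11.5% | 16.6% |
| 1.06 SD | week 6 | 5.4% | 6.3% | 8.1% | 10.4% |
| 0.65 SD | week 3 | 5.5% | 6.9% | 9.4% | 13.0% |
| 0.65 SD | week 6 | 5.1% | 5.5% | 6.1% | 7.0% |

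**5. Other conditions.**
- Effect fully maintained: carrying forward adds no bias.
- All arms improve by 0.5 SD at week 3 and 1.06 SD at week 24, with 40% lost under lf-rTMS and 10% under placebo: the bias is -(0.40 - 0.10) × (1.06 - 0.50) = -0.17 SD, against lf-rTMS.
- Week-3 effect 1.06 SD that fades, with patients who improved more lost more often (38% lost under lf-rTMS, 20% under placebo): LOCF shows 0.43 SD and 23% false positives.

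**6. Alternative method.** With the 1.06 SD fading effect and base loss settings of 20% or 40%, random or depending on week-3 improvement, multiple imputation from baseline, week 3 and arm gave a difference of about 0.00 SD and 4.6-5.1% false positives. LOCF in the same simulations gave 0.21-0.62 SD and 9-41%.

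**7. Why the planned check misses it.** A patient lost after week 3 has completed the intervention, so the completer set keeps that patient. The repeated analysis also stops at week 3.

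**8. Function scores.** Section 5.3 and the schedule grid in 9.1.1 show no week-3 GAF, SOFAS or UPSA-brief in groups 1-3. The event list in 9.1.1 and section 9.3.4 do list them. On the first reading, a patient lost after week 3 carries a baseline function score, which pulls the arms together. The formula in step 3 therefore applies clearly only to SRRS, PANSS and BNSS.

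**The case against.** The scope of the rule is partly inferred. Section 7.4 places LOCF beside discontinuation during the intervention, and the pilot work in 3.1.7 used it for response after 15 sessions, so the authors may have had only week 3 in mind. That is possible, but the wording covers all final analyses and nothing else is offered for week 24.

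A reader might infer that the protocol expects effects to last no longer than 2-4 weeks, so that any benefit at 6 months must be false. The documents do not say that. The sentence in 2.2 sits in the risk categorisation, sets no upper limit and is not an efficacy forecast for the SRRS; hypothesis 4b expects benefit at 6 months. What stands is narrower: LOCF presupposes the answer to an open question.

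The direction is also conditional. Section 3.1.4 says symptoms tend to improve with treatment, and section 8.7 expects relevant changes from concomitant treatment. The week-6 visit means some lost patients carry a later score, which reduces the bias. Section 8.5 invites patients who withdrew consent to the 6-month interview, which may reduce loss but does not change the rule. The t-test is illustrative; the plan specifies repeated-measures ANOVAs and crosstabs. Aim 4 is descriptive in wording, and the primary endpoint is untouched. All this limits the size and weight of the point without removing it.

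**Conclusion.** The point holds as a gap in the follow-up analysis. The unrestricted rule can enter a week-3 or week-6 symptom score at week 24, and the planned sensitivity analysis would not show it.

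A false lasting benefit needs two things: a week-3 advantage that fades (or comparators that catch up), and real loss after treatment. Across the assumed effects of 0.65-1.06 SD with no true week-24 difference, false-positive rates are about 5-6% at 10% loss, 6-10% at 20%, 6-16% at 30% and 7-25% at 40%. The lower ends apply when all losses follow the week-6 visit with half the effect left.

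The documents do not support saying that loss to follow-up will produce a false benefit, that the bias must favour lf-rTMS, or that function scores are affected in the same way. The 21-week gap is for groups 1-3 only; the waiting group ends treatment at week 6, 18 weeks before week 24.

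**What to change.** - State in 11.5, and align 7.4, that no earlier score is carried into the follow-up visits.
- Analyse SRRS, PANSS, BNSS and function at follow-up with a likelihood-based mixed model on observed scores, or with multiple imputation using baseline, earlier visits and arm.
- Define the waiting group's visits by its own schedule (weeks 6, 9 and 24), or limit the follow-up comparison to groups 1-3, which contain the comparators named in hypotheses 4a and 4b.
- Derive week-6 and week-24 responder status from observed or multiply imputed scores, not carried ones. Counting observed ratings alone can itself be biased if loss depends on response.
- Report the number observed per arm and visit.
- Add one missing-not-at-random sensitivity analysis at week 24.
- Reconcile section 5.3 and the 9.1.1 grid with the 9.1.1 event list and 9.3.4 on whether function is assessed at week 3.

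No new data are needed, and SPSS, already named in 11.4.2, fits the mixed model. The cost is wider week-24 confidence intervals, which reflect the information actually collected, and a little more analysis work.
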